### **3) Weight**

The weight ranges on this card are for a person of your height. Obesity makes it harder to control diabetes and places a person at increased risk for several medical problems including high blood pressure, arthritis and even some cancers. [Read only the statement coinciding to the participant's value.]

- Your weight is in the “normal” range for your height. This is considered a healthy weight. Starting or continuing healthy habits now can help prevent future weight gain and help you to maintain this healthy weight.
- Your weight is in the “overweight” range, which puts a person at higher risk for going on to become obese. Fortunately, incorporating healthy behaviors now can help prevent future weight gain.
- Your weight is in the “obese” range. The extra weight makes it is harder to control diabetes and increases the risk of heart disease and other diseases. Fortunately medical studies have shown that even a drop of 5% of body weight can lower the risk for developing many of these problems.

### **4) You may want to talk to your doctor...**

- If all values are in the “Excellent/Good” ranges: You are doing great. You may want to talk to your doctor about healthy habits to keep yourself healthy.
- [Read list of conditions in the “Concerning/Take Action” ranges.]

#### **REMINDER**

***Living Well personnel should not offer medical advice. If participants have questions more in depth than what has been stated in this script, they should be referred to their doctors.***

### **Purpose of the Research**

---

We are asking you to take part in a research study. This research study will test if Peer Advisors can help patients with diabetes better care for his or her diabetes to improve blood sugar levels, blood pressure, and quality of life. Peer advisors come from the same community as participants and have been trained to help people with diabetes. This study will enroll 500 participants. 250 participants will work with a peer advisor for 6 months and 250 participants in the general education group will receive health education videos. Which program you receive will depend on a random assignment process.

### The information that you collect will help us:

- Better understand the day-to-day experiences of individuals living with diabetes.
- Determining what effects the project has on the health and well-being of study participants.

### During today’s session you will collect (in this order):

- Informed Consent
- Blood pressure
- Hemoglobin A1c
- LDL Cholesterol
- Height & weight
- Medication names, doses, and frequencies
- Provide the participant with information on their first contact with their Peer Advisor and provide them with the report card.

*This packet is a guide to help you gather the data in a standard and reliable way.*

**Remember to complete each page, fill out each blank, and check each item off on the list as you complete them.**

Use this packet along with the Living Well Biometric Protocol, v. 2016-May24

It is very important that you do not rush and the data that is collected is accurate. Document if anything unusual happens or if it was necessary to make changes to any of the protocol in the “Notes” sections.

### Supplies:

*At the end of the day, note any supply items that are running low.  
Complete the Supply Request Checklist and fax to UAB: [contact] or call UAB.*

**At any point during the data collection a question arises,  
STOP and CALL the study manager at [contact]**

Data Collector NAME:	
Date of Data Collection:	
Client PID:	
Client Name:	

**Client Contact Information**

*(Update as needed)*

**Telephone Numbers:**

--

**Mailing Address:**

--

**Directions / Notes:**

 Data Collection in the Home / Residence	 Data Collection in the Community Venue Venue Name / Location: _____

**Data Collection Time**

Start Time	□	□	:	□	□	AM or PM		End Time	□	□	:	□	□	AM or PM
-------------------	---	---	---	---	---	----------	--	-----------------	---	---	---	---	---	----------

***Greet client and ask where would be a good location to set up for data collection.***

The data collection area will need:

- 1 electrical plugs
- Area to set-up table and chair. ***Client must be able to rest his or her arm on the table.***
- Quiet area with privacy
- Not in direct sunlight

*Supplies - Beginning of each day, make sure you have all of these items.*

General Equipment:

- Informed Consent forms
- Data Collection Packet
- Extra Medication Lists
- Extra batteries: Double A and Triple A
- Biohazard and trash bags

Blood Pressure Measurement Supplies:

- Watch / clock
- Tape measure, eyebrow pencil
- Blood pressure monitor
- Blood pressure cuffs (regular, large, extra-large)

HBA1c and LDL-Cholesterol Measurement Supplies:

- A1c NOW Test kits (doublecheck that you have enough tests for that day)
- Cardiochek PA machine, Capillary tube, and test strips
- Lancet, alcohol wipes, bandaids, gloves, gauze, waste container

Height and Weight Measurement Supplies:

- Scale
- Stadiometer
- Step stool

Program Materials:

- DVD players and Signature log
- Client Specific Study Packet (General Health Program / Living Well Program)

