Great! We are almost through. Thank you so much for answering these questions. Let me tell you a little more about the study. 
 
- Living Well program is a research study that partners a team at the University of Alabama at Birmingham with Peer Advisors in several Alabama Black Belt communities.
 
- We want to find ways to improve health outcomes in people who have diabetes.
 
- There is no cost for you to be part of this program.
 
	

- This is a 6 month project. During the 6 months, you will meet with the UAB study team 2 times in person and complete a telephone interview 2 times.
- If you are assigned a peer advisor, you will speak with your peer advisor 13-16 times over a period of 6 months.
- If you do qualify and enroll in the study, you will receive a portable DVD player, educational materials, and a \$20 VISA giftcard for participating in the study.
- At each in-person data collection visit with the UAB study team, the staff will do a finger stick test to check your A1c number, which is your average blood sugar level, and your blood cholesterol. They will also measure your height, weight, blood pressure, and make a list of your medications.
- Do you have any questions about this program?

S15. Are you interested in enrolling in the study?

**Not interested in study** → Would you mind telling me the reason you are not interested in the program?  
 [Note reason not interested here] \_\_\_\_\_

**Interested in study** → Continue to next section

Great! Let me tell you the next steps for enrolling in the program.

- I will need to schedule a time for a study research assistant to call you to complete a telephone interview with you. The telephone interview will take about 45-60 minutes to complete.
- After the interview is complete, we will schedule a time for your first in-person data collection visit.
- We ask that you do not drink any caffeine (from coffee, tea, or soda), eat, do any heavy physical activity, smoke, or ingest alcohol for 30 minutes prior to the in-person data collection visit.
- Since this is a research study, we will ask you to sign an informed consent form during the in-person visit. Even though the program does not involve any experimental medicines or procedures, we still need your consent.

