## **Medication List**

The investigators and Peers require an accurate list of medications taken by the participants. This is a seemingly simple task, but can actually be challenging because participants may bring in medications they no longer take, not bring their insulin, take their medications in a way different than written on the prescription, or not bring their medications with them. There are special instructions for aspirin and insulin below.

The biometrics personnel must:

1. Generate as accurate a medication list as possible
2. Keep one copy for the researchers, make a copy for the participant, and if the participant is assigned a Peer, make a copy for the Peer

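### The In-person Data Collection Form implies that the collector knows the arm before written consent and the baseline biometrics, and it contains no step at which the assignment is made or revealed

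*Combined protocol and SAP*

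**What the plan says.** The form's Supplies list opens with the instruction "Supplies - Beginning of each day, make sure you have all of these items". Under Program Materials it asks for a "Client Specific Study Packet (General Health Program / Living Well Program"). These are the names of the two arms.

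The form's contents list, introduced by "session you will collect (in this order"), runs: informed consent, blood pressure, A1c, LDL cholesterol, height and weight, medications. Its last item is "Provide the participant with information on their first contact with their Peer Advisor and provide them with the report card". The telephone eligibility script (Appendix D) agrees on the signature: "we will ask you to sign an informed consent form during the in-person visit".

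The visit closes with two alternative sets of instructions, one for participants in the Living Well program and one for those in the General Health Program. In the Biometric Protocol (Appendix F, Medication List), staff keep a copy of the list, give one to the participant and, "if the participant is assigned a Peer, make a copy for the Peer".

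On assignment itself, the consent text (Purpose of the Research) says only "Which program you receive will depend on a random assignment process". The pages available give no time point, unit or concealment method, and no statement on whether collectors are blinded.

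**The concern.** A packet can be specific to a client, as between two programs, only if that client's program is already settled. If the collector holds it before the visit, assignment comes before the written signature and every biometric baseline value, and the person obtaining them can see the arm.

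Two things would be at stake:

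- **Selection.** Someone who declines to sign at the visit would be lost after assignment, in front of a collector who knows the arm. Such losses can differ between arms in number or in kind, and randomisation no longer protects against that.
- **Measurement.** Some baseline steps depend on the operator: enforcing the five-minute rest and restarting it after an interruption, repeating discrepant weights, and asking whether each medicine is taken as written on the bottle. These would be done unblinded, and they form the baseline for the six-month comparison.

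No measurement in the visit needs the arm. Its first uses are the Peer's copy of the medication list and the hand-over of the packet.

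**Working it through.** No sample size, power or error rate enters this point, and the plan states no figure to reproduce. The check is to rebuild the sequence from the documents and see where assignment can fall.

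1. **Eligibility call (Appendix D).** Assignment is mentioned only conditionally: the person may be paired with a Peer Advisor. A consent form is then mailed.
2. **Telephone interview (Appendix E, items C2 to C3).** The consent form is reviewed section by section and verbal consent to the interview is taken. The baseline questionnaire follows.
3. **Scheduling (Appendix E, items F1 to F5).** The in-person visit is booked with a script that does not mention the arm.
4. **Start of the collection day (Supplies list).** The collector checks for the client-specific, arm-named packet.
5. **Visit, in its stated order.** Written consent, blood pressure, A1c, LDL, height and weight, medication list.
6. **End of visit.** Report card, then one of two arm-specific hand-overs.

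Assignment must precede step 6, because the hand-over depends on it. Between steps 4 and 6 the form has no randomisation number, envelope, call for the arm or time of assignment. Collectors are told to complete every page and tick every item, so an intended reveal step would be expected there. The hand-over instructions presume that the arm is known. The form has a single field for the data collector's name, so the person who takes consent and measures is also the person who hands over the packet.

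With the packet line at step 4, the most natural place for assignment is before step 4, and so before the signature and the biometrics. Nothing shows the arm to be known at steps 1 to 3.

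| Baseline element | Position | Arm knowledge implied? |
|---|---|---|
| Verbal consent and telephone questionnaire | Before the visit | Not shown |
| Booking of the visit | Before the visit, arm-neutral script | Not shown |
| Written consent | First item of the visit | Yes, by the packet line |
| Blood pressure, A1c, LDL, height, weight, medication list | After the signature | Yes, by the packet line |

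**The case against.** **The timing is inferred.** No sentence available says when or by whom assignment is made. Only the second of the document's two parts was available, and a randomisation section may stand in the first. The slash in the supply line could simply list the two packet types to carry, or packets might be sealed and opened later. This stands as a limit on certainty. Against it, the packet is described as specific to the client, and the form gives no instruction to choose or open one after measurement. If the first part does place assignment after baseline, this form disagrees with it and still needs editing.

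**Consent was partly given earlier.** This is correct. The form was reviewed by telephone and verbal consent to the interview was given. Only the signature and the biometrics fall at the visit. A reader might infer that the whole baseline phase follows assignment. The documents do not support that, because the questionnaire is finished before the visit.

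**No route to selective scheduling is shown.** A reader might also infer that staff know the arm while they book visits. The booking script is arm-neutral, and no visible step tells the participant the arm before hand-over. What remains is possible influence by the collector at signing.

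**Measurement bias is limited.** Blood pressure, A1c, LDL and weight are digital readings. The form records the start of the rest and the reading times, and it sets a repeat rule for weight. This stands, and leaves only the operator-dependent steps listed above.

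**Conclusion.** The point holds as a strong implication of the form. As written, it most naturally has the collector knowing the arm before the signature and the baseline biometrics, with no reveal step and no statement that collectors are blinded. The telephone interview and verbal consent are outside it.

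The size cannot be derived from the documents. One might assume that 5% to 20% of 250 per arm fail to attend or sign: 0.05 × 250 = 12.5 and 0.20 × 250 = 50. That range is an assumption, and it does not measure the bias. It counts total loss per arm rather than a difference between arms. It also uses 250, which is the planned number enrolled per arm and not the number scheduled. The importance of the point does not depend on it.

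The conclusion rests on two assumptions: that the packet line means what it appears to mean, and that no section in the unavailable part overrides the form. It is a cheap improvement that closes an avoidable route to selection and to unblinded measurement. It is not a demonstrated bias.

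**What to change.** State in the protocol when, by whom and in what unit assignment is made, how it is revealed, and whether collectors are blinded at baseline. Then bring the form into line.

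**If assignment is individual:**

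- Replace the client-specific packet line in the Supplies list with *one packet of each program* for each client due that day.
- Add a step after the medication list. With consent signed and all measurements recorded, the collector opens a sealed, numbered envelope or calls the study manager to learn the arm.
- Only then hand over the matching packet and, for the peer arm, make the Peer's copy of the medication list.
- Count a person as randomised from that step.

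**If assignment is by cluster, or deliberately earlier:** an envelope at the visit does not apply. Make the form agree with the protocol, give the reason for the timing, and report refusals and non-attendance after assignment by arm.

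The cost is a few extra packets per trip, one envelope or call per visit, and an edit to the form. The change protects baseline only. The collector still learns the arm at hand-over, so blinding at the six-month visit has to be settled separately.

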## Step 1: Blood Pressure

- Gather materials – BP cuff, BP monitor, tape measure, eyebrow pencil, alcohol wipe
- Check the BP monitor’s battery life and change batteries or plug-in to a wall socket if available
- Squeeze all air from the BP cuffs
- Select arm (right arm, unless there is a reason to avoid measurement in this arm)
- Arm is bare to the shoulder

### Client position

- Standing, facing away from you, arm bent at the elbow at a 90-degree angle (Hand on stomach)

### Measure the arm

- Measure from the top of the shoulder (acromion / bony prominence of the shoulder girdle) to the tip of the elbow (olecranon process)
- Mark the midpoint on the back of the arm. At the mark, measure the circumference of the arm

Arm Circumference   .  cm

- Select correct cuff size.

Arm Circumference	Bladder Size	Cuff selected
24 – 35.5 cm	Regular / Medium	
36 – 42 cm	Large	
> 42 cm	Extra large	

- Client is seated comfortably in a chair with a back; both feet flat on the floor
- Arm is supported & resting comfortably on the table at a 90-degree angle with the palm facing up
- Room is quiet with no distractions

### Apply cuff

- Find and mark the brachial artery with the eyebrow pencil
- Place cuff around the upper arm, approximately at heart level
- Wrap cuff snugly on the arm, inner bladder of cuff over the area of the brachial artery (insert first joint of two fingers under the cuff)
- Arm is resting on table with palm facing up and connect cuff to the monitor

Arm Used:  Left Arm  
 Right Arm

5 minute rest time begun   .   AM or PM

BP Measurement 1	BP Measurement 2
Time 1   .   AM or PM	Time 2   .   AM or PM
BP 1    Pulse 1   	BP 2    Pulse 2   
  	  

notes:

**Remember! 1-minute rest is needed between measurement 1 and 2.**

## Step 2: Hemoglobin A1c and LDL Cholesterol Measurement

- ❑ Gather materials - gloves, lancet, gauze, alcohol wipe, band-aid, A1c NOW kit (3 items: machine, cartridge, & dilution kit) and cholesterol (Cardiochek PA machine, test strips, capillary tubes and plunger, test strips).

[figure not shown]
Before pricking finger, note time: 

--	--

 . 

--	--

 AM or PM

[figure not shown]
**Too Little**  
Add More

**Just Right**

**Too Much**  
Wipe Away

### Collect Sample for A1c

- ❑ Open dilution kit
- ❑ With alcohol wipe, clean finger, & allow alcohol to dry
- ❑ Use lancet, dispose into sharps bag
- ❑ Wipe away first drop of blood with gauze
- ❑ Use 2nd drop for the test. Collect blood sample by gently touching blood drop with collector to fill.
- ❑ Fully insert blood collector into Sampler Body. Shake well 6-8 times. Stand sampler on table.

### Prepare Cartridge

- ❑ Open Test Cartridge packet. **IMPORTANT: Use the cartridge within 2 minutes.**
- ❑ “Click” cartridge into place. Monitor and Test Cartridge codes must match.
- ❑ When display says “SMPL”, the monitor is ready.
- ❑ Ensure monitor is on a level surface.
- ❑ Remove base from the blood collector.
- ❑ Push down blood collector on the cartridge completely to dispense sample. Remove quickly.
- ❑ **Do not handle the monitor again until test is complete.**

### Recording the results

- ❑ results will display in 5 minutes.
- ❑ 3 items will be displayed: “QCOK” (QC test results), “00.0” (test results), “00TL” (# of test left)

Refer to the anthropomorphic protocol, page 11 for any error codes.

A1c	

		

 . 

	

				notes:  

Remember:

- Machines should not be direct sunlight or near cold or heat sources
- Do not open the A1c NOW test kit materials until you are ready to begin that portion of the test
- Once test begins, do not move the machine until the test is complete

(PID: \_\_\_\_\_)

### Step 3: LDL-Cholesterol Measurement

❑ After A1c test is being analyzed, collect sample for cholesterol machine.

#### Collect Sample for Cholesterol Test

- ❑ With alcohol wipe, clean finger, & allow alcohol to dry
- ❑ Use lancet, dispose into sharps bag
- ❑ Wipe away first drop of blood with gauze
- ❑ Use 3rd drop for the test. Collect blood sample by gently touching blood drop with capillary tube to fill to the black line on the tube.
- ❑ Deposit the sample on the test strip of the Cardiochek PA machine.
- ❑ **Do not handle the monitor again until test is complete.**

#### Recording the results

❑ Results will display in approximately 2 minutes.

[figure not shown]
LDL	
 
 			
 
				notes:

#### Remember:

- Machines should not be direct sunlight or near cold or heat sources
- Prepare the Cardiochek PA machine (insert test strips in the machine, lay out capillary tube and plunger) before A1c test is started.
- Once test begins, do not move the machine until the test is complete

[figure not shown]
Insert MEMo Chip with finger notch (top) side up, lot number code facing down.

- 1) Collection:**  
Place your thumb and finger just under the bulb
- 2) Deposit:**  
Place your thumb and finger on the bulb.  
Cover the air holes and gentl expel the sample

Deposit the entire sample  
**Do not touch the testing surface**

[figure not shown]
Touch the tip of the capillary tube to the drop of blood  
Fill completely to the black line with no air bubbles

## Step 4: Height and Weight Measurement

- Gather materials - scale, stadiometer, step stool
- Check scale battery and replace if needed, calibrate on yourself

### Set up

- Scale and stadiometer is placed on level, uncarpeted floor
- Stadiometer – assemble by matching shapes on each segment
- Stadiometer’s horizontal bar is correctly placed on the vertical rod.

ORBITALE: Lower margin of eye socket  
 TRAGION: Notch above tragus of ear or at upper margin of zygomatic bone at that point  
 FRANKFORT PLANE: Orbitale-tragion horizontal line

### Body Position

#### Height measurement

- Standing straight, not slouching, at the center of the foot plate
- Heels together, back against height rod
- Back, buttocks, heels touching height rod

### Head Position

- Head is positioned correctly (Does not need to be touching the height rod)
- Client is looking straight ahead, ear and top of cheek bone should be level with the ground  
**Ask client to raise or lower chin as needed**
- Horizontal bar is lowered firmly onto the top of the head - may need to alter hair styling to make contact with the top of the scalp

### Measurement

- Ask client to breathe in deeply → “Take a deep breath”
- Just before client exhales, note the reading on the stadiometer → “Breathe out”
- MEASURE IN CENTIMETERS**
- Repeat measuremet. **If the measurement is different by .04 cm, repeat both measurements.**

Height 1      CM	Height 2      CM
notes:	
 not needed.    Height 3      CM	 not needed.    Height 4      CM

### Alternative Position - Client unable to place heels, buttocks, and back on the vertical height rod.

- Position client so that only the buttock & possibly the shoulders are in contact with the vertical rod
- It is important that these clients are standing straight and tall, legs together as much as possible with the buttock in contact with the vertical height rod.

### Alternative Position - Clients with severe spine curvature

- Curvature of spine should touch the rod with the heels and buttocks
- If this is not possible, turn pt to the side, so the side of arm & shoulder is in contact with vertical rod

